8.1. Data management

The data will be included in the case report form (CRF) that will be provided by the investigator to the promoter anonymously, using a numbering system. To trace to which group the patient belongs (sham or verum), the device number will be collected in the CRF as well.

8.2. Statistics

8.2.1. Sample size

Results from a randomized controlled trial on an acute migraine treatment (6) showed in the placebo group a reduction in mean pain score of 10% after 1 hour and 14% after 2 hours, compared to baseline. The results of the pilot trial on the acute treatment of migraine using the Cefaly® device showed a reduction in mean pain score of 59% after 1 hour and 55% after 2 hours. The standard deviation related to mean pain score was 2.42 after 1 hour and after 2 hours. Based on these results we could assume a difference in mean pain score of 2.83 after 1 hour and 2.40 after 2 hours between the active and placebo groups. A minimum of 17 patients in each group would be statistically required to detect a significant difference in mean pain score after 1 hour and after 2 hours, with a power of 80% and at two-sided alpha level of 5%, using a t-test for two independent samples.

A previous study reported 71% of patients from the placebo group using rescue medication compared to 41.33% for active groups on average (7). Considering these percentages, 43 patients in each group would have been statistically required to detect a significant difference in rescue medication use after 24 hours with a power of 80% and at two-sided alpha level of 5%, using a proportion test for two independent samples.

Overall, at least 43 patients in each group should allow to detect a significant difference between active and placebo groups in mean pain score after 1 hour and after 2 hours, and in rescue medication use. As the trial will be conducted in three different centres, the number of patients is rounded to 45 in each group (i.e. 15 patients per group and per centre). Consequently, 90 patients will be recruited.

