4.2.3. Post-treatment phase

Two hours after the beginning of the treatment the patient will have to give a new estimate of the pain on the VAS, provided that the patient didn't take a rescue medication before.

After the 2 hours, if needed usual rescue treatment can be administrated to the patient. If so, this is recorded by the investigator.

Patients will also be instructed to record the pain level 24 hours after the beginning of the treatment. They will be contacted to report this pain level and whether or not rescue medication was taken within the 24 hours following the beginning of the treatment. In case of rescue medication intake within the 24 hours following the treatment the pain level at 24 hours will not be taken into account.

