6.7. Device provisioning

The promoter will deliver the specific devices directly to the investigators. The devices will be delivered by sets of even number of verum and sham devices, ensuring at least one device per patient. The investigator will not be able to distinguish both. A single device cannot be reused on different patients. Each device will bear a unique number that has to be reported in the patient's CRF and will allow to identify, at the end of the study, whether the patient used a sham or verum device. Electrodes will be delivered in enough quantity to ensure to have one per patient.

7. Practical study modalities

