7.3. Blinding

Blinding between verum and sham devices has been previously validated in a trial on 128 patients (62 verum and 66 sham). A new device will be used for each study patient. Sham and verum stimulators and electrodes will look alike. Verum will use a high frequency impulse and sham a low frequency. Both devices will generate paresthesia on the forehead to ensure blinding. Patients will therefore not be able to know if it is the active neurostimulation or the sham.

The investigator and research coordinator will be blinded from which device the patient has (sham or verum). A built-in electronic system will record the treatment delivered to each patient.

The treatment allocation will be concealed using the following procedure. Verum and sham stimulators will be programmed by the manufacturer Cefaly Technology. They will be sent to each investigator by blocks with equal number of verum and sham devices. The only indication on the device box will be a

number. The list of correspondence will be sent in a sealed envelope to the investigators. This procedure ensures a blinding from the enrolling investigator as well.

8. Data management and statistics

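### Devices are allocated in balanced blocks within each site, but no site-adjusted analysis is specified; adding one costs almost nothing and gains precision on rescue use if sites differ

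*Combined protocol and SAP*

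**What the plan says.** Allocation is by site. Section 7.3 says of the stimulators: "They will be sent to each investigator by blocks with equal number of verum and sham devices". Section 6.7 is similar: "The devices will be delivered by sets of even number of verum and sham devices". Section 8.2.1 sets 45 per group as "15 patients per group and per centre", which implies three centres. Section 4.1 lists 4 investigation sites.

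Tests are named only in 8.2.1. Pain is sized with a two-sample t-test (17 per group). Rescue within 24 hours is sized on "71% of patients from the placebo group using rescue medication compared to 41.33% for active groups on average", for 80% power at a two-sided 5% level, "using a proportion test for two independent samples", giving 43 per group. Rescue is the larger requirement, so it sets the size of the trial, although section 3 lists it as secondary. The primary outcome is the change in pain at 1 hour.

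Section 8.2.2 covers descriptive summaries, last value carried forward, and the ITT and per-protocol sets. It names no inferential test, model, covariate or stratification factor.

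On rescue itself, section 4.2.3 says that after 2 hours "if needed usual rescue treatment can be administrated to the patient".

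**The concern.** Balancing the arms within each site takes site differences out of the treatment contrast. A test that ignores site still counts those differences as random error. If sites differ, its standard error is too large, its true type I error falls below the nominal 5%, and it has less power than a test that uses site.

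Rescue use is the outcome where this could show. It depends on each site's usual practice and on perceived need, and no common rule for giving it is stated, so rates may differ between sites for reasons unrelated to the device. It also has the least power in reserve: about 82% at 45 per group, against more than 99% for pain.

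Because 8.2.2 is silent, the choice to adjust for site is also left open until the data are in hand.

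**Working it through.** **Inputs from 8.2.1.** Rescue 71% (placebo) and 41.33% (active); two-sided alpha 5%, power 80%; pain differences 2.83 (1 h) and 2.40 (2 h); SD 2.42; 45 per group as 3 centres x 15 per group.

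**Assumed.** The spread of rescue rates between sites, which the documents do not give.

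**1. The plan's own figures.** With pooled variance and no continuity correction,

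n = [1.960 x sqrt(2 p(1-p)) + 0.842 x sqrt(p1(1-p1) + p2(1-p2))]² / (p1-p2)²,

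where p = (0.71 + 0.4133)/2 = 0.56165 and p1-p2 = 0.2967. This is (1.375 + 0.564)² / 0.0880 = 42.7, so 43 per group reproduces. The same formula gives 82.1% power at 45 per group.

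For pain, the noncentral t with difference 2.40 and SD 2.42 gives 16.98, so 17 reproduces. Power at 45 per group is 99.6% for 2.40 and 99.98% for 2.83.

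**2. Rescue, pooled test against stratified test.** Trials were simulated with 3 sites x 15 per arm and average rates held at 71% and 41.33%. The odds ratio was common to all sites, and site intercepts were equally spaced on the logit scale. The pooled z-test was compared with the Cochran-Mantel-Haenszel (CMH) test by site, without continuity correction.

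| Sham rescue across sites (assumed) | Power, pooled | Power, CMH | Pooled SE too wide by |
|---|---|---|---|
| 71% at every site | 81.4% | 81.3% | 0% |
| 61-81% | 81.7% | 83.0% | about 1% |
| 51-88% | 82.8% | 87.3% | about 6% |
| 42-94% | 84.3% | 91.2% | about 12% |

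A repeat with 200,000 trials per row agreed within about 0.2 point. With 4 sites x 11 per arm (44 per arm) and sham rescue 50-88%, power is 82.0% pooled and 85.6% stratified. With 4 such sites and no site differences, stratifying costs about 0.6 point.

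**3. Type I error.** With a common null rate of about 56% (the mean of the two planned rates), the pooled test's true level is 4.6%, 4.1%, 3.1% and 1.9% down the four rows; CMH stays between 4.6% and 5.0%. With 71% in both arms, the pooled level is about 4.0% at the 51-88% spread and 2.9% at 42-94%. The direction is the same and the effect milder.

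**4. Pain.** With total SD fixed at 2.42 and a fraction r of variance due to site, the unadjusted SE is too wide by a factor 1/sqrt(1-r): 1.054 at r = 0.10 and 1.118 at r = 0.20. At the planned 2.40, power without and with site is 99.7% and 99.8% at r = 0.10, a gain of under 0.1 point. At 2.83 both exceed 99.9%. Adjustment can narrow the confidence interval, but at the planned differences there is almost no power left to gain.

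**The case against.** **The tests are planning tests.** An unstratified formula is ordinary for sizing and does not rule out a stratified analysis. This stands. A reader might infer that the plan commits to pooled tests, but 8.2.2 commits to no test. What can be said is that site handling is unspecified and that the only tests named do not use it.

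**No planned power is lost.** A reader might infer that the trial is undersized. The documents do not support that: at the planned average rates the pooled test has 81-84% power in every 3-site scenario, above its 80% target. The shortfall is only relative to a better test. Nor does ignoring site inflate false positives; when sites differ, the error is in the conservative direction.

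**The effect depends on an unknown.** With no site differences nothing is gained, and at moderate spread the gain is about 1 point. The larger figures need sham rescue rates spanning 37 points (51-88%) or 52 points (42-94%) across three sites. This stands, and is why the size is given as a range.

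**The primary outcome is hardly touched.** This also stands at the planned differences.

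**Balance within site may be imperfect.** Section 4.2.1 removes patients who cannot tolerate the first minutes after a device has been allocated. Section 8.2.2 excludes those with early rescue or no 1-hour score. Block size is not stated, and blocks may end incomplete. This weakens exact balance but does not argue against stratifying, which also handles the resulting imbalance between sites.

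**Conclusion.** The point holds as an inexpensive improvement, not as an error in the sample size or a threat to the primary conclusion. Allocation is 1:1 in blocks within site, and nothing in the documents carries site into the analysis. If rescue use differs between sites, an unstratified analysis is conservative. For the secondary 24-hour rescue outcome the power forgone is between 0 and about 7 points.

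That range rests on assumed site spreads, a common odds ratio, equal site sizes and complete within-site balance. The mechanism is certain; its size in this trial cannot be known from the documents.

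**What to change.** First reconcile the number of sites between sections 4.1 and 8.2.1, since it defines the strata. Then add to 8.2.2:

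- For both rescue outcomes (2 hours and 24 hours): a Cochran-Mantel-Haenszel test stratified by site, with the Mantel-Haenszel risk difference and its 95% CI.
- For change in pain score: a model with treatment and site as fixed effects.

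Neither N nor section 8.2.1 needs to change. The cost is two lines of text and at most 3 degrees of freedom (4 sites minus 1). If sites do not differ, the price on rescue is about 0.1 point of power with 3 sites, or about 0.6 point with 4 sites of 11 per arm. No new data are needed, as each patient's site is known. The wording should be fixed before unblinding.

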8.2.2. Statistical methods

- All relevant general, safety and efficacy data will be descriptively summarized at each time point.
- Continuous data will be summarized by the number of subjects (N), the arithmetic mean, the standard deviation, the coefficient of variation as a percentage (CV%), the median, the inter-quartile range, the minimum and the maximum value.
- Categorical data will be summarized by absolute (N) and relative (%) frequency tables.
- Where considered as relevant, the study data will also be graphically depicted.

- Imputation of missing data will be performed according to the last value carried forward method.
- Analyses will be conducted on an intent-to-treat (ITT) basis, i.e. including all subjects who used the study device for more than 4 minutes (see in exclusion criteria 8. Allodynia), did not take rescue medication before the 1 hour and reported pain at 1 hour.
- A sub-analysis of the per-protocol patients (those receiving the complete 1-hour treatment) will be performed as well.

9. Management of adverse events

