- Since March 2015, an open-label pilot trial on the acute treatment of migraine using the Cefaly® device has been underway at Columbia University, NY. Patients experiencing a migraine attack for at least 3 hours (without use of acute medications during this time) and having stable pain intensity for at least 1 hour, are eligible to receive a 60-minute stimulation to treat their attack. Pain is assessed on a 10-point visual analogue scale (VAS) before, after the 1-hour treatment, and 2 hours after the beginning of the treatment. The study is still on-going, but the results to date confirm prior observations that e-TNS therapy via the Cefaly® device can significantly reduce pain intensity during an acute migraine attack, as measured via the VAS.

Based on the data from the above studies and preliminary findings from the open-label pilot trial at Columbia, it is reasonable to further investigate the efficacy of e-TNS with the Cefaly® device as an acute treatment for migraine via a double-blind, randomized, sham-controlled trial.

2. Study objective

The main objective of this study is to assess the efficacy of the Cefaly® device as an acute treatment of migraine attack in adult patients.

3. Study outcomes

Primary outcome:

- Mean change of pain score at 1 hour compared to baseline

Secondary outcomes:

- Proportion of patients not having required rescue medication at 2 hours
- Mean change of pain score at 2 hours compared to baseline (if rescue therapy was not used)
- Proportion of patients not having required rescue medication within 24 hours
- Mean change of pain score at 24 hours compared to baseline (if rescue therapy was not used)

4. Study design

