4.1. General description

This study is a clinical study with the following characteristics:

- Multi-center (4 investigation sites)
- Prospective
- Double-blind
- Sham-controlled
- Randomized

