4.2.1. Recruitment phase

Two options are available to recruit patients:

- Eligible patients can be recruited during a standard care visit if they are experiencing a migraine attack having lasted at least 3 hours, with pain stabilized for at least 1 hour, and have not used acute migraine medication within the past 3 hours.
- Patients can also be screened beforehand (having been informed about the study at a standard visit or via advertisement), and arrange for an on-demand appointment when they are undergoing an attack for at least 3 hours, with pain stabilized for at least 1 hour.

Patient will receive the information and consent documents and have to sign these documents before study procedures are initiated. Then the investigator will verify that the patient meets all inclusion criteria and none of the exclusion criteria. If this is the case, the patient has to give a value on an 11-point visual analog scale (VAS) (0 = no pain, 10 = maximum pain) of the current pain associated with the migraine attack.

The patient will then be randomized to either the verum or the sham group. To this end, a unique device will be allocated to him/her.

The investigator will then apply the device on the patient and start the stimulation. If the patient cannot bear the paresthesia of the neurostimulation (needs to stabilize intensity before 4 minutes i.e. nociceptive threshold < 5 mA for impulse width of 250 μ s), the patient is considered meeting the exclusion criteria of allodynia (too low nociceptive threshold). The patient is in this case not included in the trial.

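### Section 8.2.2 states no between-group analysis of the primary outcome; an ANCOVA on baseline pain and site would use data already collected, at no cost in patients

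*Combined protocol and SAP*

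**What the plan says.** Section 3 defines the primary outcome as "Mean change of pain score at 1 hour compared to baseline".

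Section 8.2.2 is the whole of the statistical methods. It opens with "All relevant general, safety and efficacy data will be descriptively summarized at each time point" and goes on to list summary statistics, graphs, last value carried forward, an analysis set labelled ITT and a per-protocol sub-analysis. It contains no hypothesis test, between-group estimate, confidence interval, covariate or centre term.

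The only test named for pain is in Section 8.2.1, as the basis for the sample size. The number there is what is needed to "detect a significant difference in mean pain score after 1 hour and after 2 hours", "using a t-test for two independent samples". Nothing says that this is also the planned analysis.

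Two design features bear on the choice of analysis. Under Section 4.2.1 the patient scores current pain on the 11-point scale before being randomised. Section 7.3 says of the devices: "They will be sent to each investigator by blocks with equal number of verum and sham devices".

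**The concern.** A randomised efficacy trial should fix in advance the comparison that produces its primary result. Here the outcome, the time point and the two-sided 5% planning level are given, but the comparison has to be inferred from the sample-size paragraph.

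If the inferred t-test is used, information already in hand is left out. A t-test on change uses baseline pain only by subtraction, which assumes a slope of 1 between baseline and 1-hour pain. Site plays no part, although allocation is balanced within site. At stake are some precision, protection of the primary estimate against chance baseline imbalance, and a primary analysis that a reader can check against the plan.

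**Working it through.** **Plan's own figures.** Inputs from 8.2.1: differences 2.83 (1 hour) and 2.40 (2 hours), SD 2.42, 80% power, two-sided 5%. The noncentral-t calculation gives 12.5, so 13 per group, at 2.83, and 16.98, so 17 per group, at 2.40. The stated 17 reproduces and is driven by the 2-hour difference. With 45 per group, a t-test on 1-hour score has power 99.98% at 2.83.

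**Where the planned differences come from.** The pilot and placebo reductions from baseline are 59% and 10% at 1 hour, and 55% and 14% at 2 hours. So 2.83 / (0.59 - 0.10) = 5.78 and 2.40 / (0.55 - 0.14) = 5.85. Both point to a common baseline near 5.8, so the planned differences are differences in reduction from baseline. Under randomisation, score and change have the same expected group difference.

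**Assumptions, not in the documents.** s1 = 2.42 is the SD of the 1-hour score; baseline SD s0 = 1.5, 1.8 or 2.42; baseline-to-1-hour correlation rho = 0.3, 0.5 or 0.7; n = 45 analysed per arm.

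**Formulas.**
- Var(change) = s0² + s1² - 2·rho·s0·s1
- Var(ANCOVA) = s1²·(1 - rho²)·[1 + 1/(2n - 4)]. The last factor is the cost of estimating the slope: 1 + 1/86 = 1.0116.
- Saving = 1 - Var(ANCOVA)/Var(change)
- 95% limit of chance baseline imbalance: L = 1.96·s0·√(2/45) = 0.62, 0.74 and 1.00 points for the three s0
- Shift of the unadjusted change difference at that limit = (1 - rho·s1/s0)·L

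| s0 | rho | Var(change) | Var(ANCOVA) | Saving | Shift (points) |
|---|---|---|---|---|---|
| 1.5 | 0.3 | 5.93 | 5.39 | 9.1% | 0.32 |
| 1.5 | 0.5 | 4.48 | 4.44 | 0.7% | 0.12 |
| 1.5 | 0.7 | 3.02 | 3.02 | 0.1% | -0.08 |
| 1.8 | 0.3 | 6.48 | 5.39 | 16.8% | 0.44 |
| 1.8 | 0.5 | 4.74 | 4.44 | 6.3% | 0.24 |
| 1.8 | 0.7 | 3.00 | 3.02 | -0.8% | 0.04 |
| 2.42 | 0.3 | 8.20 | 5.39 | 34.2% | 0.70 |
| 2.42 | 0.5 | 5.86 | 4.44 | 24.1% | 0.50 |
| 2.42 | 0.7 | 3.51 | 3.02 | 14.0% | 0.30 |

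The largest saving, worked through: Var(change) = 5.856 + 5.856 - 2(0.3)(2.42)(2.42) = 8.199; Var(ANCOVA) = 5.856 × 0.91 × 1.0116 = 5.391; 1 - 5.391/8.199 = 34.2%.

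**95% CI half-width at rho 0.5**, t × SD × √(2/45), with 88 df for change and 87 for ANCOVA: 0.886 to 0.883 (s0 1.5), 0.912 to 0.883 (1.8), 1.014 to 0.883 (2.42).

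**Power of the unadjusted t-test on change.** The least favourable cell is s0 2.42, rho 0.3, where the SD of change is √8.199 = 2.86. Power there is 97.6% at 2.40 and 99.6% at 2.83.

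**Site term.** Four sites use 3 df, so the residual df go from 87 to 84. The t quantile rises from 1.9876 to 1.9886, a ratio of 1.0005, so the interval widens by 0.05% if site explains nothing.

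**Score or change in the model.** Subtracting baseline from the outcome lowers the baseline coefficient by exactly 1 and leaves the treatment coefficient unchanged. With baseline as a covariate, both outcomes give the same treatment estimate and interval.

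**The case against.** The strongest reply is that the t-test in 8.2.1 is the evident intended analysis, that it is valid if fixed in advance, and that the trial has ample power without adjustment. Equal device blocks per site already limit imbalance between arms by site. The ANCOVA gain is uncertain: once slope estimation is allowed for, it is nil or slightly negative when rho is high and baseline SD is 1.5 or 1.8. The larger savings arise mainly where baseline SD is set equal to 2.42. All of this stands, and it makes the adjusted model an improvement rather than a correction.

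Two stronger readings are tempting. First, 8.2.1 speaks of mean pain score and says "The standard deviation related to mean pain score was 2.42 after 1 hour and after 2 hours", while Section 3 speaks of change. A reader might infer that the sponsor is free to test scores or changes and report the better, with an inflated error rate. The documents do not support this. Section 3 fixes change at 1 hour as primary, the planning differences derive from reductions from baseline, and nothing suggests that both tests would be run. What the SD of 2.42 describes is not fully clear, but that affects only the planning precision.

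Second, a reader might infer that the trial is too small or the sample size miscalculated. The 17 per group reproduces, and 45 per group is far above it for pain.

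**Conclusion.** The point holds as an improvement at no cost in data or patients. Section 8.2.2 states no between-group comparison for an otherwise well-defined primary outcome. The only candidate test leaves site unused and baseline pain under-used.

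The benefit is a fixed primary analysis, an estimate protected against chance baseline imbalance (up to 0.70 points in the scenarios tried), and a precision effect that could be negligible or substantial. No defect in sample size or power follows.

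The sizes rest on an assumed baseline SD and correlation, on 2.42 being the 1-hour score SD, and on all 45 per arm being analysed. The last is optimistic, because Sections 4.2.1, 4.2.4 and 8.2.2 allow exclusions after a device is allocated. The case for stating the analysis does not depend on any of these assumptions.

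**What to change.** Add to 8.2.2, before unblinding: the primary analysis is an ANCOVA of 1-hour change in pain (equivalently, 1-hour score) on treatment, baseline pain and site, tested at two-sided 5%, reporting the adjusted difference between arms with its 95% CI. Keep the unadjusted t-test on change as a sensitivity analysis. State whether the SD of 2.42 refers to scores or to changes.

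Before fixing the site factor, reconcile the number of centres: Section 4.1 gives four, while Section 8.2.1 gives three with 15 patients per group in each. The total of 90 need not change.

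The cost is a few sentences and at most 4 residual degrees of freedom (88 to 84): one for baseline and up to three for site. No new data and no more patients are needed.

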4.2.4. Drop-outs, intention-to-treat and last value carried forward

a) During the treatment one-hour phase

If the patient takes rescue medication before 1 hour, it is a drop-out because the action of the medication affects the pain estimate at 1 hour.

If the patient stops the one-hour treatment and leaves the clinic, it is a drop-out because there is no pain estimate at 1 hour.

If the device stopped working accidentally, it is a drop-out because of technical reason.

On the other hand, if a patient does not get the full Cefaly acute treatment (does not want to complete the 1 hour stimulation), but stays available for the 2 hours of the protocol, this patient is kept in the trial and considered as an intention-to-treat patient (as opposed to per protocol patient).

b) During the post treatment phase

If the patient takes rescue medication before 2 hours, only the one-hour pain intensity estimate has been measured; the last value carried-forward method will be applied for 2 and 24 hours pain intensity estimate.

If the patient takes rescue medication at 2 hours or after 2 hours, the last value carried-forward will be applied for the 24 hours pain intensity estimate.

[figure not shown]

Figure 1 - Study flowchart

5. Subjects

The study will include 90 men or women.

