7.1. Measures

Pain score. In order to evaluate the modification of pain score from baseline to 1-hour treatment and to 2-hour treatment, patients will be asked to give an indication on the pain level using a visual analogue scale (VAS) counting eleven levels (0 = no pain, 10 = maximum pain) at the recruitment phase (before applying the treatment), right after the treatment phase (1 hour), 2 hours after the beginning of the treatment and at 24 hours after the beginning of the treatment.

Rescue medication after the treatment. The investigator will also record whether the patient uses another acute medication right after the 2 hours. Patients will also be contacted 24 hours after the beginning of the treatment to report whether or not rescue medication was taken within the 24 hours following the beginning of the treatment.

The following table depicts when the different measures will be made:

	Baseline	1 hour	2 hours	24 hours
Pain score	●	●	●	●
Rescue medication intake			●	●

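### A patient with no recorded rescue who is not reached at 24 hours keeps the 2-hour pain score, so the 24-hour pain difference is pulled towards the 2-hour difference

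*Combined protocol and SAP*

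**What the plan says.** Section 8.2.2 of the combined protocol and SAP states: "Imputation of missing data will be performed according to the last value carried forward method". It makes no exception for any outcome or time point. The only additional analysis it plans is per-protocol.

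Section 3 lists as a secondary outcome "Mean change of pain score at 24 hours compared to baseline (if rescue therapy was not used"). Section 7.1 schedules the last two pain scores at "2 hours after the beginning of the treatment and at 24 hours after the beginning of the treatment", with none in between. For the 24-hour score, section 4.2.3 relies on patients recording their pain at home and says "They will be contacted to report this pain level and whether or not rescue medication was taken within the 24 hours". Pain and rescue use at 24 hours thus come from a single contact.

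Section 4.2.4 has its own carry-forward rules, but only for patients who take rescue: "If the patient takes rescue medication at 2 hours or after 2 hours, the last value carried-forward will be applied for the 24 hours pain" estimate. Section 4.2.3 treats the same patients differently: "In case of rescue medication intake within the 24 hours following the treatment the pain level at 24 hours will not be taken into account".

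The intention-to-treat set in section 8.2.2 requires more than 4 minutes of device use, no rescue before 1 hour and a 1-hour pain score. It does not require a 24-hour score.

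**The concern.** A patient with no recorded rescue and no 24-hour report is outside the rescue rules of section 4.2.4 but inside the analysis set. The general rule is then the only one that applies, and the last available score is normally the 2-hour score. The rule therefore states that this patient's pain at 24 hours equals the pain at 2 hours. Migraine pain can resolve or return over 22 hours.

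The gap is foreseeable. Baseline, 1-hour and 2-hour scores fall within the supervised session, while the 24-hour score depends on a later contact.

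At stake is what the 24-hour pain outcome can show. It is meant to tell whether an early difference lasts, and each carried value assumes that it does. If the effect fades, part of the 2-hour difference reappears as a 24-hour difference.

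**Working it through.** **Inputs from section 8.2.1.** The plan assumes "a difference in mean pain score of 2.83 after 1 hour and 2.40 after 2 hours", an SD of 2.42, 45 patients per group, and rescue use of 71% (placebo) and 41.33% (active).

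**Inputs not in the documents.** These are the fraction m of patients not reached at 24 hours and the true 24-hour difference D24. Both are varied below.

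**The plan's own figures.** For two means, n per group = 2 × (1.960 + 0.842)² × 2.42² / 2.40² ≈ 16 by the normal approximation. The t-test calculation gives 16.98, so 17, as stated. The 2.83 difference alone needs 13, so the 2-hour difference sets the figure. For rescue, 71% against 41.33% gives 43 per group without continuity correction, also as stated. The planning inputs can therefore be used as they stand.

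**Bias.** Suppose the same fraction m is unreached in each group, for reasons unrelated to pain. The expected 24-hour difference after carry-forward is (1 − m) × D24 + m × 2.40. Subtracting D24 gives

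bias = m × (2.40 − D24).

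| D24 (assumed) | m = 5% | 10% | 20% | 30% |
|---|---|---|---|---|
| 0 | 0.12 | 0.24 | 0.48 | 0.72 |
| 1.2 | 0.06 | 0.12 | 0.24 | 0.36 |
| 2.40 | 0 | 0 | 0 | 0 |
| 3.0 | −0.03 | −0.06 | −0.12 | −0.18 |

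Positive values favour the device.

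**How many patients contribute.** Section 3 restricts the outcome to patients without rescue. At the planning rates that is 45 × (1 − 0.4133) = 26.4 active and 45 × (1 − 0.71) = 13.05 sham, or about 26 and 13. At m = 10%, about 2.6 active and 1.3 sham scores would be carried forward.

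**Effect on a test, extreme case D24 = 0.** The plan names a two-sample t-test for pain at 1 and 2 hours only, so a t-test at 24 hours is an assumption. The check used 20,000 simulated trials with normal scores, SD 2.42 and two-sided 5%. Each score was replaced with probability m by one carrying the 2.40 difference.

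| Patients analysed | m = 10% | 20% | 30% |
|---|---|---|---|
| 26 active, 13 sham (no rescue) | about 5% | about 8% | 11 to 12% |
| 45 and 45 | about 7% | about 14% | about 26% |

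The second row holds only if all 45 per group have a score and none is carried forward for rescue.

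**Standard error.** With 45 per group and m = 20%, the estimated difference had an empirical SD of about 0.53, and the mean reported standard error was 0.528. The two agree, so the excess rejections come from bias.

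**The case against.** The strongest case on the other side is that this is small and rests on assumed figures. No non-contact rate is given, no 24-hour difference is given, and the test results use the extreme case of 2.40 points falling to zero. At 10% missing among patients without rescue there is almost no inflation. The outcome is secondary, and section 8.2.2 names no test for it. All of this stands, and it limits the size of the point. It does not remove the rule, whose effect is zero only if the 2-hour difference persists.

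A second objection also stands. Rescue status and pain come from the same contact, so an unreached patient's rescue status is known only up to about 2 hours. Such patients can be described only as having no recorded rescue, and a repair cannot sort them into rescue users and others.

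A reader might infer more than the documents support:

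- That carry-forward makes the standard error too small. The check above does not show this; each patient still contributes one measured score.
- That the false-positive rate is 14% at 20% missing. That figure needs 45 scored patients per group with none carried forward for rescue. Sections 3 and 4.2.3 leave rescue users out, and section 4.2.4 would carry their scores forward.
- That the rule always favours the device. It does so only if the difference shrinks after 2 hours.
- That all evidence on duration is compromised. The 2-hour outcomes are measured an hour after stimulation ends and are untouched by this gap.

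**Conclusion.** The point holds for the secondary 24-hour pain outcome. Under the general rule in section 8.2.2, an unreached patient with no recorded rescue contributes a 22-hour-old score. The resulting bias is m × (2.40 − D24): 0.24 points at 10% missing and 0.48 at 20% if no true difference remains at 24 hours, and about half that if D24 is 1.2.

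This assumes equal missingness in both groups, unrelated to pain. It also assumes that the planning difference of 2.40 applies to the patients analysed at 24 hours; the documents give no separate 2-hour figure for patients without rescue. In the extreme case, a t-test at 24 hours would reject falsely in about 5% and 8% of trials among patients without rescue.

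The 1-hour primary outcome is not affected, because the analysis set requires an observed 1-hour score. The change should be made before unblinding, but the primary conclusion does not depend on it.

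**What to change.** In section 8.2.2, stop using last value carried forward as the main method for 24-hour pain scores that are missing because the patient was not reached. Use one of:

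- multiple imputation by group from the baseline, 1-hour and 2-hour scores; or
- a repeated-measures mixed model of observed scores with group, time, group by time and baseline pain.

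Keep the carried-forward result as a sensitivity analysis only. State that rescue status after 2 hours is unknown for unreached patients and is not to be read as no rescue. Report the number unreached per group.

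Before fitting either method, reconcile section 4.2.4, which carries pain forward after rescue, with sections 3 and 4.2.3, which leave 24-hour pain out after rescue. Carried-forward rescue values should not enter the model as if observed.

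The cost is a revised paragraph, a little more programming and possibly a slightly wider 24-hour interval. No new data or patients are needed.
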